
STUDY DESIGN:
 
This is a multicenter, phase II study evaluating the efficacy and safety of the combination of lenalidomide and eltrombopag in low risk MDS.
	

Patients will be treated based on their baseline platelet counts:

Arm A: Patients with platelet counts $\geq 50k$ at baseline:

These patients will start Len at 10mg/d for 3 weeks/month, and will not start eltrombopag until the platelet counts drop below 50,000. If platelets drop less than 50,000, Len will be stopped and eltrombopag will be started at a dose of 100mg initially (50 mg for subjects of East Asian heritage) and titrated up to a maximum dose of 300 mg (150 mg for subjects of East Asian heritage) to achieve a platelet count above 50,000/L. Once a platelet count above 50,000 is achieved, the same dose of eltrombopag will be continued for an additional two weeks. Once a platelet count $> 50,000$ is maintained for two weeks, eltrombopag will be discontinued and Len will be started as a single agent. If the platelets again fall below 50,000 then Len will be stopped and eltrombopag will be re-initiated at the dose that was last given to the patient. Once the platelets are increased to above 50,000 and maintained at this level for 2 weeks, Len will be started again and this time will be given concurrently with eltrombopag. These agents will subsequently be used concurrently for all subsequent cycles.

Arm B: Patients with Plts $< 50k$ at baseline

These patients will not receive Len initially. Eltrombopag will be started alone at a dose of 100mg initially and titrated up (Table 4) to achieve a platelet count above 50,000. Once the platelet count above 50,000 is achieved, the same dose of eltrombopag will be continued for an additional two weeks. Once the plt count $> 50,000$ is maintained for two weeks, the patients will discontinue eltrombopag and follow the treatment algorithm described for patients in arm A.

[figure not shown]

Figure 1: Schema of the study (* starting dose of Eltrombopag for Asian subjects is 50mg)

STUDY ENDPOINTS

Primary:

Hematologic improvement

Secondary: Time to attain and duration of hematologic improvement Bone marrow morphologic and cytogenetic response Platelet counts and Bleeding events
	

STUDY DURATION:2 years
	
TOTAL SAMPLE SIZE:52patients

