2 SCHEDULE OF STUDY ASSESSMENTS

	Screening Assessment (30 days prior to initiation)	Weekly	Every 28 days (Day 1 of each cycle)	Week 16 and treatment discontinuation	Follow up ¹¹
Medical History	x				
Prior MDSTreatment	x				
ECOG Performance Status	x	X ⁸	x		
Pregnancy test ¹	x ²		x ³	X	
Serum ferritin level	x			X	
Serum erythropoietin	x				
Thyroid function tests ⁴	x			X	
aaPT/PTT/INR	x				
Serum chemistry ⁵	x	X ⁸	x	X	
Hematology, peripheral blood smear and RBC transfusion history ⁶	x ⁷	x ⁸	x	X	x
Physical examination	x		x	x	x
ECG	x		x ¹²		
Review medication log			x		
Response				x	

assessment ⁹					
Bone marrow aspirate & biopsy ¹⁰	X			X	
Cheek swab and toe nail clipping	X				

1. Women of childbearing potential only. Serum or urine pregnancy testing for β-HCG with a sensitivity of at least 50 mIU/mL. For further requirements for pregnancy testing and birth control, please see Appendix 1.
					

2. Within 7 days prior to the first day of study therapy.
					

3. Every 4 weeks while on study drug.
					

4. TSH (thyroid-stimulating hormone), T3, and T4 levels. Repeat thyroid function tests every three months.
					

5. Includes sodium, potassium, chloride, CO₂, calcium, magnesium, phosphorus, blood urea nitrogen (BUN), creatinine, glucose, albumin, total protein, alkaline phosphatase, total bilirubin, aspartate transaminase (SGOT/AST) or glutamic pyruvic transaminase (SGPT/ALT), lactate dehydrogenase (LDH), and uric acid.
					

6. Red blood cell (RBC) count, reticulocyte count, hemoglobin, hematocrit, white blood cell (WBC) count and differential, absolute neutrophil count (ANC), and platelet count required for protocol therapy must be done < 24 hours prior to the treatment cycle. Pretreatment CBC with differential and LFT's should be done < 1 week before randomization.
					

7. If not obtained within 7 days of the first day of study therapy, repeat the CBC on Day 0 of study treatment prior to start of study therapy.
					

8. Perform weekly for 4 weeks, then every 2 weeks for 5 to 8 weeks and monthly thereafter. Weekly CBC should be done when titrating or starting eltrombopag dosing until a stable platelet count is achieved.
					

9. Hematologic, pathologic, and cytogenetic response will be assessed according to criteria outlined in Section 6.1.2.
					

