8.1.2 Dose Modifications

Dose Reductions for lenalidomide

Table 1 gives the dose levels for the dose reduction steps for adverse events.

Table 1: Dose Reduction Steps for lenalidomide

Starting dose 10 mg/day on days 1-21, followed by 7 days of no therapy

Dose level -1 5 mg daily

Dose level -2 5 mg every other day (qod)

Patients who experience limiting neutropenia after prolonged treatment with 5 mg every other day may resume treatment at the same dose upon hematologic recovery.

Dose Modifications for Neutropenia

Hold lenalidomide for a decline in neutrophil count to $< 500/\mu\text{L}$ that does not respond to myeloid growth factor administration. Lenalidomide should be resumed at the next dose

reduction step when neutrophil count is $> 500/\mu\text{L}$. **Dose Modifications for Thrombocytopenia**

For patients with a baseline platelet count $< 50,000/\mu\text{L}$;

Start eltrombopag when the platelet count is $< 50,000/\mu\text{L}$. Start Lenalidomide (AND STOP eltrombopag) only after platelet count $> 50,000$ (non transfused) for at least 2 weeks. If platelet fall $< 50,000/\mu\text{L}$ after resuming lenalidomide again then again hold dose and start Eltrombopag again. Once plt count $> 50,000$ for two weeks, then start lenalidomide and give eltrombopag concomitantly.

For patients with a baseline platelet count $\geq 50,000/\mu\text{L}$;

Start Lenalidomide alone. If plt count falls below $50,000/\text{L}$ then follow algorithm as above.

Patients who do not experience platelet recovery within 8 weeks of starting Eltrombopag should be removed from study and complete all off study evaluations.

Dose modifications for hemoglobin levels:

For those patients experiencing a rise in hemoglobin $> 14 \text{ g/dL}$, Lenalidomide should be withheld until the hemoglobin is $< 12 \text{ g/dL}$, at which time treatment can be resumed according to the dose adjustment recommendations in Table 1. For those patients previously adjusted to the lowest CC-5013 (lenalidomide) dose, the CC-5013 (lenalidomide) schedule should be changed to a 2 week treatment schedule every 4 weeks.

Dose Modifications for Other Adverse Events

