Endocrine	Hyperthyroidism or hypothyroidism	
 Interrupt CC-5013 (lenalidomide) and initiate appropriate medical therapy. Resume CC-5013 (lenalidomide) at investigator's discretion (maintain dose level).
Cardiac Arrhythmias	Sinus bradycardia/other cardiac arrhythmia Grade 2	
 Hold (interrupt) dose. Follow at least weekly. If the toxicity resolves to \leq grade 1 resume at next lower dose level.
	\geq Grade 3	
 Discontinue CC-5013 (lenalidomide) study drug.
Other Toxicity	Other non-hematologic toxicity assessed as CC-5013 (lenalidomide)-related \geq Grade 3	
 Hold (interrupt) dose. Follow at least weekly. If the toxicity resolves to \leq grade 2 resume at next lower dose level.

[figure not shown]
Dosing for Eltrombopag

Patients will initially be started on 100 mg eltrombopag (50 mg for subjects of East Asian heritage). Thereafter, dependent on the platelet response (see Table 3 below), the dose of study medication can be increased every 2 weeks, up to a maximum dose of 300 mg/day (150 mg/day for subjects of East Asian heritage).

Modified dosing for subjects of East Asian heritage (i.e., Japanese, Chinese, Taiwanese and Korean) has been implemented for the following reasons. In healthy Japanese subjects, plasma eltrombopag AUC(0- τ) was approximately 80% higher when compared to non-Japanese healthy subjects who were predominantly Caucasian. Similarly, in patients with ITP, plasma eltrombopag exposure was approximately 70% higher in East Asian (i.e., Japanese, Chinese, Taiwanese and Korean) subjects as compared to non-East Asian subjects who were predominantly Caucasian.

Intra-individual dose adjustments will be made in a stepwise fashion, by sequentially increasing to dose levels of 100 mg, 200 mg or 300 mg as needed (50, 100, 150 mg for subjects of East Asian heritage). Titration of study medication with different dosages on different days will be permitted where needed in order to maintain a stable platelet count in the safe range without exceeding platelet counts >400 Gi/L. The dosing regimen of eltrombopag must be individualized based on platelet counts. Use the lowest effective dosing regimen to maintain platelet response.

Figure 4: Schema of dose adjustments for eltrombopag

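### No rule in the available text ties weekly blood counts to the restart of lenalidomide together with eltrombopag, so the first concurrent cycle can run with few or no required counts once a site calls the platelet count stable

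*Combined protocol and SAP*

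**What the plan says.** **The restart.** If platelets fall below 50,000 again, lenalidomide stops and eltrombopag is re-initiated at its last dose. Section 1 (Arm A) continues that once platelets are back above 50,000 and "maintained at this level for 2 weeks, Len will be started again and this time will be given concurrently with eltrombopag". Section 8.1.2 has the same step: "after resuming lenalidomide again then again hold dose and start Eltrombopag again", and after two weeks above 50,000, "then start lenalidomide and give eltrombopag concomitantly". Neither section attaches a count frequency to the restart.

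**Routine counts.** Footnote 8 of the Section 2 schedule reads "Perform weekly for 4 weeks, then every 2 weeks for 5 to 8 weeks and monthly thereafter". Footnote 6 adds a count within 24 hours before each treatment cycle. The schedule also has a week-16 column that includes hematology.

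**Extra counts, by trigger.**
- Starting or titrating eltrombopag (footnote 8): "Weekly CBC should be done when titrating or starting eltrombopag dosing until a stable platelet count is achieved". Section 8.1.2 repeats the weekly rule until stability and then goes to monthly.
- An eltrombopag dose adjustment (Section 8.1.2): at least weekly for 2-3 weeks.
- High platelets (Section 8.1.2, dose-adjustment table): at 200-400 k/uL, either a dose decrease or weekly counts; above 400 k/uL, twice-weekly counts.
- Stopping eltrombopag (Section 9.2): weekly for at least four weeks.
- A stable eltrombopag dose (Section 9.2): monthly.

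**The concern.** The hold rule at 50,000 works only when a count is taken. Every patient at the concurrent restart has already fallen below 50,000 after lenalidomide, and this is the first cycle on the combination. The platelets that qualify the patient for restart were measured with lenalidomide held, so they say little about the count once it resumes. Section 3.4 reports thrombocytopenia in 57% of patients in the first cited lenalidomide study, where it was dose limiting.

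The plan monitors the comparable moments more closely. The first four study weeks have weekly counts. The first lenalidomide restart, as a single agent, follows the stopping of eltrombopag and so falls under the four-week rule in Section 9.2. At the concurrent restart eltrombopag continues, and that rule does not apply. A fall could then go unseen while lenalidomide is still being taken, with a risk of bleeding. Platelet counts and bleeding events are also secondary endpoints, so sparse counts would thin the data on the combination.

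**Working it through.** The plan gives no figure to reproduce. The check asks how many counts the text obliges a site to take inside the first concurrent cycle.

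**Assumptions.** Restart is day 1 of a 28-day cycle at study week R. Footnote 8 runs from study entry (the plan does not state its starting point). The site regards the count as stable at restart. There is no later eltrombopag dose change, and platelets stay below 200 k/uL. The monthly count is the same sample as the pre-cycle count unless stated otherwise.

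**Footnote 8 calendar.** The middle phase can be read in two ways.
- Shorter (two-weekly during weeks 5 to 8): counts at weeks 1, 2, 3, 4, 6, 8, then monthly.
- Longer (two-weekly for up to 8 further weeks, 4 + 8 = 12): counts at weeks 1, 2, 3, 4, 6, 8, 10, 12, then monthly.

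**Required counts on days 2-28**, i.e. those at a week w with R < w < R + 4. A week-16 visit kept on the calendar falls on cycle day 7 × (16 − R) + 1.

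| Restart week R | Shorter | Longer | Week-16 visit on calendar | Required |
|---|---|---|---|---|
| 7 | 1 (week 8) | 2 (weeks 8, 10) | outside | 1 or 2 |
| 8 | 0 | 1 (week 10) | outside | 0 or 1 |
| 9 | 0 | 2 (weeks 10, 12) | outside | 0 or 2 |
| 10 | 0 | 1 (week 12) | outside | 0 or 1 |
| 11 | 0 | 1 (week 12) | outside | 0 or 1 |
| 12 | 0 | 0 | day 29, outside | 0 |
| 13, 14, 15 | 0 | 0 | days 22, 15, 8: 1 | 0 or 1 |
| 16 or later | 0 | 0 | day 1 or earlier | 0 |

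The 0 at weeks 13-15 arises if the week-16 visit moves with delayed cycles. From week 16, a site that keeps monthly counts on their original four-weekly calendar, and not on cycle day 1, would have at most 1. Weekly counts would give 3 (days 8, 15, 22).

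**Dose-adjustment rule.** Suppose the last adjustment precedes the two maintenance weeks. For the first eltrombopag course, Section 1 says "the same dose of eltrombopag will be continued for an additional two weeks". At most 3 − 2 = 1 week of that run is then left at restart, enough for one count at day 8.

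**When restarts occur.** Let each fall and each rise take k weeks, and add two maintenance weeks per eltrombopag course. The value of k is assumed; for scale, Section 8.1.2 says "the dose of study medication can be increased every 2 weeks".
- Arm A: fall, rise, 2, fall, rise, 2 = 4k + 4, giving weeks 8, 12, 16, 20 for k = 1, 2, 3, 4.
- Arm B by Section 8.1.2: rise, 2, fall, rise, 2 = 3k + 4, giving weeks 7, 10, 13, 16.
- Arm B by Section 1, where "the patients will discontinue eltrombopag and follow the treatment algorithm described for patients in arm A" in full: 5k + 6, giving weeks 11, 16, 21, 26.

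**Upper bounds on delay.** If platelets fall just after the pre-cycle count and the next required count is at day 29, detection takes up to 28 days. That span includes up to 21 lenalidomide days on the starting schedule. With weekly counts the maximum is 7 days.

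**The case against.** The best reply is that weekly counts are already running at the restart. Eltrombopag has just been re-initiated, and the weekly rule ends only when a stable count is reached. Section 8.1.2 links stability to a safe range and to desired levels, so declaring it on the day lenalidomide returns is not the most natural reading. That is fair, and a careful site would carry on weekly. But the term has no definition, two weeks above 50,000 is exactly the condition for restart, and nothing obliges a site to continue.

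Several other points stand and limit the size:
- The week-16 hematology visit can supply one count for restarts at weeks 13-15.
- The starting point of footnote 8 is an assumption, and it matters most in Arm B, where lenalidomide begins after entry.
- The fixed dose over two maintenance weeks is stated only for the first eltrombopag course. An adjustment near or after the restart brings a new weekly run of 2-3 weeks.
- Platelets of 200 k/uL or more bring closer checks.
- Figures 1, 4 and 5 are not shown, and the titration schema that Section 5.1 borrows from another study is not available. A monitoring rule could sit in any of them.
- Patients still being transfused may have counts taken for that reason.

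None of these is an obligation, in the text that can be read, triggered by the concurrent restart itself.

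**Conclusion.** The gap holds for the concurrent restart and should be closed. Under the stated assumptions the plan requires 0-2 counts inside the first concurrent cycle for restarts at weeks 7-11, 0 at week 12, 0 or 1 at weeks 13-15, and 0 from week 16 (at most 1 with monthly counts on their original calendar).

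Three stronger readings are tempting and are not supported. A reader might infer that lenalidomide restarts in general go unmonitored; Section 9.2 covers the single-agent restart. A reader might infer that no count is ever required mid-cycle after week 12; the week-16 visit, dose changes and high platelet counts can each require one. A reader might take 28 days, or 21 dosing days, as the expected delay; both are ceilings that need a stable call, no dose change and a fall soon after restart. The documents give no rate for a second fall, so no share of patients can be stated.

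**What to change.** Amend footnote 8 of Section 2 and the matching monitoring sentence in Section 8.1.2 (Dosing for Eltrombopag). Require a weekly CBC with differential for at least four weeks after each concurrent restart of lenalidomide with eltrombopag that follows a platelet hold, whether or not the count is considered stable.

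The cost is protocol wording plus up to 3 extra routine CBCs per restart (days 8, 15 and 22); day 29 is already the next pre-cycle count. Where the existing schedule supplies counts, fewer are added: 3 − 2 = 1 to 3 − 0 = 3 at weeks 7-11, and 2 or 3 at weeks 13-15. Restarts after holds for other reasons, the sample size and the analysis are unchanged.

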
10. Bone marrow aspirate and biopsy with cytogenetic analysis and iron stains will be performed pre-study, and after 16 weeks of study treatment, and at the time of final response analysis. Additional biological studies obtained with bone marrow aspiration
					

are summarized in Section 14.

11. Every 3 months if patient is < 2 years from study entry, every 6 months if patient is 2-5 years from study entry, every 12 months if patient is 5-10 years from study entry. No specific requirements if patient is more than 10 years from study entry.

12. Only for patients receiving 300 mg eltrombopag dose or higher, resting 12-lead ECG will be obtained pre-dose on Day 1. A post-dose ECG should be obtained at Tmax (3 hours); if assessment cannot be performed at 3 hours, record actual time ECG was performed within a 2-6 hour window post-dose. A pre- and post-dose ECG as described above is required Week 2, week 4, 8 and 16.

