4 STUDY OBJECTIVES AND ENDPOINTS

4.1 Objectives

4.1.1 Primary Objectives

- To evaluate the rate of hematologic improvement of the eltrombopag/lenalidomide combination (as per Modified IWG criteria)
- To evaluate the safety and tolerability of the combination

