5 INVESTIGATIONAL PLAN

5.1 Overall design

This is a multicenter, Phase II study evaluating the efficacy and safety of the combination of lenalidomide and eltrombopag in low risk MDS. This study will include patients with low risk MDS (IPSS low and Int-1) with symptomatic anemia or transfusion dependence. Patients will be treated in 2 separate arms based on their baseline platelet counts:

Arm A : Patients with platelet counts $\geq 50k$ at baseline:

These patients will start Len at 10mg/d for 3 weeks/month, and will not start Eltrombopag until the platelet counts drop below 50,000. If platelets drop less than 50,000, Len will be stopped and Eltrombopag will be started at a dose of 100mg initially and titrated up (similar schema to 509 study) to achieve a platelet count above 50,000. Once the platelet count above 50,000 is achieved, the same dose of Eltrombopag will be continued for an additional two weeks. Once a platelet count $> 50,000$ is maintained for two weeks, Eltrombopag will be discontinued and Len will be started as a single agent. If the plts again fall below 50k then Len will be stopped and Eltrombopag will be re-initiated at the dose that was last given to the patient. Once the platelets are increased to above 50,000 and maintained at this level for 2 weeks, Len will be started again and this time will be given concurrently with Eltrombopag. These agents will now be used concurrently for all subsequent cycles.

Arm B: Patients with Plts $< 50k$ at baseline

These patients will not receive Len initially. Eltrombopag will be started alone at a dose of 100mg initially and titrated up (similar schema to 509 study) to achieve a

platelet count above 50,000. Once the platelet count above 50,000 is achieved, the same dose of eltrombopag will be continued to additional two weeks. Once the plt count > 50,000 is maintained for two weeks, the patients will discontinue eltrombopag and follow the treatment algorithm described for patients in arm A. Patients that never drop their platelet counts below 50,000 will not receive any additional eltrombopag. (Figure 1)

Treatment with myeloid growth factors is permitted for the management of neutropenia at the discretion of the treating investigator.

Study drugs will be continued until disease progression or unacceptable toxicities.

Bone marrow examinations will be performed at baseline, at every 4 months and at study discontinuation.

52 evaluable adult subjects with MDS will be evaluated.

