6.2 Exclusion Criteria

A subject will not be eligible for inclusion in this study if any of the following criteria apply:

1. Pre-existing cardiovascular disease (including congestive heart failure, New York Heart Association [NYHA] Grade III/IV), or arrhythmia known to increase the risk of thromboembolic events (e.g. atrial fibrillation), or subjects with a QTc >450 msec (Male) and QTc > 470 msec (Female). Patients with history of atrial fibrillations or arrhythmias may be considered if in normal sinus rhythm at the time of registration and if cardiac echocardiogram shows no evidence of any cardiac thrombus.
2. Patients determined to be at increased risk of arterial or venous thrombosis by the investigator
3. Bone marrow fibrosis that leads to a dry tap.
4. Female subjects who are nursing or pregnant (positive serum or urine β -human chorionic gonadotropin (β -hCG) pregnancy test) at screening or pre-dose on Day 1.
5. Treatment with an investigational drug within 30 days or 5 half-lives (whichever is longer) preceding the first dose of study medication.
6. Patients with documented liver cirrhosis
7. Patients with known Splenic Vein Thrombosis.

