Serum ALT, AST, and bilirubin should be measured prior to initiation of eltrombopag, every 2 weeks during the dose adjustment phase and monthly following establishment of a stable dose. If bilirubin is elevated, perform fractionation. Evaluate abnormal serum liver tests with repeat testing within 3 to 5 days. If the abnormalities are confirmed, monitor serum liver tests weekly until the abnormality(ies) resolve, stabilize, or return to baseline levels. Permanently discontinue eltrombopag if ALT levels increase to $\geq 3X$ the upper limit of normal (ULN) and are:

- progressive, or
- persistent for ≥ 4 weeks, or
- accompanied by increased direct bilirubin, or
- accompanied by clinical symptoms of liver injury or evidence for hepatic decompensation.

Pharmacokinetic evaluations in patients with hepatic impairment show that plasma eltrombopag $AUC_{(0-\tau)}$ increases with increasing degree of hepatic impairment (as measured by Child-Pugh). Exercise caution when administering eltrombopag to patients with hepatic impairment (Child-Pugh Class A, B, C). Use a lower starting dose of eltrombopag in patients with any degree of hepatic impairment i.e. cirrhosis and monitor closely

Bone Marrow Reticulin Formation and Risk for Bone Marrow Fibrosis

Eltrombopag is a thrombopoietin (TPO) receptor agonist and TPO-receptor agonists may increase the risk for the development or progression of reticulin fiber deposition within the bone marrow.

In the ITP extension study, 151 patients have had bone marrow biopsies evaluated for increased reticulin and collagen fiber deposition. Bone marrow biopsies taken after 1 year of therapy showed predominantly myelofibrosis (MF) Grade 1 or less in 140/151 (93%) of patients. There were 11/151 (7%) of patients with MF Grade 2. Four patients had collagen deposition reported. One patient with a pre-existing MF Grade 1 developed a MF Grade 2 and subsequently discontinued treatment with eltrombopag. Clinical studies have not yet excluded a risk of bone marrow fibrosis with cytopenias.

Prior to initiation of eltrombopag, the peripheral blood smear should be examined closely to establish a baseline level of cellular morphologic abnormalities. Following identification of a stable dose of eltrombopag, peripheral blood smears and CBCs should be examined monthly for new or worsening morphological abnormalities (e.g., teardrop and nucleated red blood cells, immature white blood cells) or cytopenia. If the patient

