develops new or worsening morphological abnormalities or cytopenia, treatment with eltrombopag should be discontinued and a bone marrow biopsy, including staining for fibrosis considered.

Recurrence of Thrombocytopenia After Cessation of Eltrombopag

Discontinuation of eltrombopag may result in recurrence of thrombocytopenia. This recurrence of thrombocytopenia may increase the patient's risk of bleeding, particularly if eltrombopag is discontinued while the patient is on anticoagulants or antiplatelet agents. In the 3 controlled ITP clinical studies, transient decreases in platelet counts to levels lower than baseline were observed following discontinuation of treatment in 8% and 8% of the eltrombopag and placebo groups, respectively. Serious hemorrhagic events requiring the use of supportive ITP medications occurred in 4 severely thrombocytopenic patients within one month following the discontinuation of eltrombopag; none were reported among patients in the placebo group.

Following discontinuation of eltrombopag, weekly CBCs, including platelet counts for at least 4 weeks should be obtained and alternative treatments for recurrence of thrombocytopenia, according to current treatment guidelines, considered.

Thrombotic/thromboembolic complications

Eltrombopag may increase the risk of thrombotic/thromboembolic events.. Excessive doses of eltrombopag may increase platelet counts to a level that produces thrombotic/thromboembolic complications.

In the 3 controlled ITP clinical studies, thrombotic/thromboembolic complications occurred in four patients in the groups that received eltrombopag and none in the placebo groups. Thrombotic/thromboembolic complications have also been reported in the ITP extension study. The thrombotic/thromboembolic complications in patients with chronic ITP included both venous and arterial events and were observed at low and normal platelet counts.

Use caution when administering eltrombopag to patients with known risk factors for thromboembolism (e.g., Factor V Leiden, ATIII deficiency, antiphospholipid syndrome, chronic liver disease). To minimize the risk for thrombotic/thromboembolic complications, do not use eltrombopag in an attempt to normalize platelet counts. Follow the dose adjustment guidelines to achieve and maintain a platelet count of $\geq 50 \times 10^9/L$ as necessary to decrease the risk for bleeding

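### No scheduled marrow biopsy requires a fibrosis stain or grade, so treatment-emergent fibrosis, a risk the protocol names for eltrombopag, cannot be systematically estimated

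*Combined protocol and SAP*

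**What the plan says.** Section 2, footnote 10, sets the content and timing of the marrow examinations: "Bone marrow aspirate and biopsy with cytogenetic analysis and iron stains will be performed pre-study, and after 16 weeks of study treatment", and again at the final response analysis. Section 5.1 gives a different timetable and names no stain: "Bone marrow examinations will be performed at baseline, at every 4 months and at study discontinuation".

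Section 9.2 describes the risk: "TPO-receptor agonists may increase the risk for the development or progression of reticulin fiber deposition within the bone marrow". It adds: "Clinical studies have not yet excluded a risk of bone marrow fibrosis with cytopenias". From the ITP extension study, where biopsies after one year were graded, it reports: "There were 11/151 (7%) of patients with MF Grade 2". It also describes one patient who went from a pre-existing Grade 1 to Grade 2.

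For monitoring, Section 9.2 relies on a baseline blood smear and on monthly smears and blood counts once the dose is stable. If smear morphology or a cytopenia is new or worse, eltrombopag is to be stopped and "a bone marrow biopsy, including staining for fibrosis considered".

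Section 6.2, item 3, excludes "Bone marrow fibrosis that leads to a dry tap". Section 4.1.1 lists as a primary objective: "To evaluate the safety and tolerability of the combination".

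**The concern.** The protocol names a harm, says that the risk remains open, and takes at repeated times the tissue on which that harm is graded. It does not ask for the grade.

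Two things are at stake. First, a patient can enter with fibrosis short of a dry tap and have no grade on record, so fibrosis seen later cannot be classed as new, worse or unchanged. Second, fibrosis on treatment is sought only when a smear or blood count prompts it and the investigator then chooses to stain. Progression without such a trigger goes unrecorded. A final report with no fibrosis cases would not distinguish absence of the harm from absence of measurement.

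**Working it through.** The plan states no fibrosis figure to reproduce. The check is whether any section requires a fibrosis stain or grade.

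**1. Every place where marrow or safety is specified**

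| Place | What it requires | Fibrosis stain or MF grade? |
|---|---|---|
| Section 2, footnote 10 | Cytogenetics and iron stains; pre-study, week 16, final response analysis | No |
| Section 5.1 | Marrow at baseline, every 4 months, discontinuation | No |
| Section 6.2, item 3 | Excludes fibrosis with a dry tap | No grade |
| Section 8.1.2, Figure 5 | Algorithm for blast counts (the figure itself is not in the text reviewed) | None mentioned in the text |
| Section 9.2 | Smears and counts; for-cause biopsy with optional fibrosis stain | Optional, no scale |
| Section 11 | Blast percentage, maturation, dysplasia, cytogenetics | No |
| Section 14.1 | Toxicity graded by CTCAE v4.0 | No |
| Section 16, Appendix 6 | Sequencing, flow cytometry, aspirate slides | No |

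Footnote 10 sends the reader to Section 14 for further biological studies. That section is the biostatistics; the correlative studies are in Section 16. Neither adds a fibrosis stain.

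**2. How far the for-cause route reaches**

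- The biopsy and stain are optional.
- No grading scale is named.
- No stained baseline core exists for comparison.
- One of the two triggers, cytopenia, is non-specific here. Section 3.4 reports neutropenia in 67% and thrombocytopenia in 57% as dose-limiting on lenalidomide alone, and Section 11 counts worsening cytopenias toward treatment failure. A cytopenia caused by fibrosis could be attributed to lenalidomide or to MDS.

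**3. What graded cores could show (illustrative only)**

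Inputs: 25 patients at the first stage and 52 at most (Section 14.2); the quoted ITP proportion, 11/151 = 7.3%; and assumed true rates of 2%, 5% and 10%. Every patient is assumed to take eltrombopag and to have a graded follow-up core.

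Chance of at least one MF Grade 2 case = 1 − (1 − p)^n:

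| True rate p | n = 25 | n = 52 |
|---|---|---|
| 2% | 40% | 65% |
| 5% | 72% | 93% |
| 7.3% | 85% | 98% |
| 10% | 93% | above 99% |

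If no case were seen, the exact one-sided 95% upper bound is 1 − 0.05^(1/n): 11.3% for n = 25 and 5.6% for n = 52.

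Actual exposure will probably be lower. Section 14.2 assumes that 10–20% of patients with platelets above 50,000 may never need eltrombopag. If all 52 were such patients and 20% were unexposed, 52 × 0.8 = 41.6, or about 42, would be exposed, and the bound becomes 1 − 0.05^(1/42) = 6.9%.

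The table shows only that the planned cores could be informative if stained and graded. It does not predict cases in this trial.

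**The case against.** The strongest case on the other side has five parts.

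- **A route exists.** Section 9.2 provides a for-cause biopsy. It is triggered by smear morphology as well as by cytopenia, and it is backed by baseline and monthly smears that the schedule carries out. Fibrosis found that way would be an adverse event. This stands. A reader might infer that fibrosis is never looked for, or that the safety objective cannot address it at all; the documents do not support either. What is missing is systematic measurement against a baseline.
- **Footnote 10 is not exhaustive.** It omits blast percentage and dysplasia, which Section 11 needs from the same marrow, so its silence does not prove that fibrosis goes unreported. Sites may stain for reticulin routinely, and a retained core might be stained later. This stands as a possibility, but nothing requires the stain, makes it uniform across centers or provides for keeping cores.
- **The ITP figure does not transfer.** The 11/151 is a prevalence after one year in another disease, and the protocol does not say how many of the 11 were new. Here the first on-treatment marrow is at about four months and eltrombopag may be brief and intermittent. This stands. A reader might infer from 7% that Grade 2 cases are nearly certain in this trial, or that its higher eltrombopag doses make them more likely. The documents give neither a rate for MDS nor a dose relationship for fibrosis.
- **Section 14.1 tabulates no individual harm**, so fibrosis is not singled out. True, but most harms reach the adverse event record through visits and routine laboratory tests. Fibrosis needs a stain.
- **It is a design preference.** In part: no text obliges the trial to grade fibrosis. But the protocol calls the risk unresolved and already takes the tissue.

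**Conclusion.** The concern holds in this limited form. No scheduled biopsy requires a fibrosis stain or grade, and the only fibrosis staining is for cause and optional. Treatment-emergent fibrosis therefore cannot be systematically estimated or separated from pre-existing fibrosis. Individual cases found for cause can still be reported.

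The gap affects all scheduled cores in up to 52 patients. Its existence rests on the text alone, not on any assumed rate. With graded cores, zero cases would bound the MF Grade 2 frequency at 5.6% to 11.3% for 52 down to 25 exposed and assessed patients. Without them, no bound can be given.

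Two limits remain even after the fix. Without a control group, a shift in grade could reflect the disease as well as the drug. And in patients who start on lenalidomide alone, the baseline core may precede the first eltrombopag dose by some time.

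This is a worthwhile, inexpensive improvement to the safety assessment. It does not invalidate the trial.

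**What to change.** 1. Reconcile the marrow timetable first: footnote 10 gives week 16 and the final response analysis, while Section 5.1 repeats marrows every 4 months and at discontinuation.
2. In footnote 10, add a reticulin stain, with a collagen stain if reticulin is positive, and an MF grade on a named scale. Apply it to the cores already taken at baseline, at the scheduled on-treatment marrows and at discontinuation.
3. In Section 14.1, add a table of the shift from baseline to worst on-study MF grade among patients who took eltrombopag, stating how many had both a baseline and a follow-up grade.
4. Correct footnote 10's cross-reference to Section 14 for the biological studies.

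The cost is a small laboratory charge, one line in the schedule and one table. No biopsy, visit or patient is added, and treatment rules are untouched. The stain should be specified before enrolment, because the comparison depends on the baseline core.
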